### **6.4 Replacements**

Subjects that withdraw from this study will not be replaced.

## **7 Visit Schedule, Study Procedures, Training and Data Collection**

### **7.1 Visit Schedule**

Subjects will be invited to the clinic for the following visits:

- Visit 1 – Screening
- Visit 2 – Baseline Day 1 (0 to +14 days to Visit 1)
- Visit 3 – Middle of parallel phase (week 13)
- Visit 4 – End of parallel phase (week 26)
- Visit 5 – Final Visit (week 39)
- Follow-up call (+2 to +5 days) if needed

Please refer to the overall Schedule of Assessments and the below details for each study visit.

## 7.2 Visit 1 - Screening

No study-specific procedures must be performed before informed consent has been obtained.

Study procedures include the following assessments:

- Provide information to subject - orally as well as presented in the written Subject Information Leaflet - and ensure possibility to ask questions, see section 12.2
- Obtain written Informed Consent
- Allocate subject ID number (via the eCRF-system) to each subject who has signed the informed consent form; see section 13.1.1 for details
- Assess all applicable inclusion and exclusion criteria and confirm subjects' eligibility
- Obtain and record demographics, including age, gender, race
- Obtain and record handedness, highest level of education as well as current employment status and family status
- Obtain and record diabetes background and history including insulin therapy and diabetes complications
- Obtain and record diabetes medication including but not limited to brand name(s) of insulin used, total daily dose, total basal and bolus doses, sensitivity factors, etc.
- Obtain and record relevant previous and ongoing concomitant medications
- Obtain and record relevant medical history of diseases other than diabetes
- Obtain indication for CSII
- Record HbA1c value, taken less than 2 months prior to this visit based on routine clinic practice (local laboratory)
- Perform urine pregnancy test if applicable (i.e. women of child bearing potential only. Post-menopausal status and surgical sterility to be reported as medical history)
- Record all relevant data in the eCRF
- Have subject complete questionnaires
- Randomization (in the eCRF-system) to one of the three study groups
  - Group A: Accu-Chek® Solo micropump system for 39 weeks
  - Group B: MDI for 26 weeks, then Accu-Chek® Solo micropump system for 13 weeks
- Group C: mylife™ OmniPod® for 26 weeks then Accu-Chek® Solo micropump system for 13 weeks Make appointment for next visit

Remind the subjects to bring the blood glucose meter currently used with them to the next visit.

### **7.3 Visit 2 - Baseline Day 1 (0 to +14 days to Visit 1)**

The baseline visit must take place not later than 14 days after the screening visit, and can be combined with the screening visit.

Study procedures include the following assessments:

- Obtain and record any changes in concomitant medications
- Obtain and record diabetes background and history including insulin therapy and diabetes complications
- Assess and record any AE/SAEs
- Obtain information on hypoglycemic events and time of absence from work or school due to diabetes complications
- Obtain and record weight and height
- Draw blood sample for determination of HbA1c (in central laboratory)
- Perform urine pregnancy test in women of child bearing potential (only if applicable by local law, e.g. in Austria)
- Examine insertion sites and record signs of redness, swelling, heat, pain and itching according to the categories as listed (none, minor, moderate, severe)
- Perform and document training of study devices and procedures, see section 7.9
- Perform carbohydrate counting training
- Hand-out and register study material:
  - Study device(s), consumables and other supplies
  - Create subjects' profile in Accu-Chek® Smart Pix and link assigned study device(s) with subject profile
- Provide instructions with regard to:
  - Handling of any malfunctions and contact to local Call Center (handing out call center card)
- Make appointment for the following visit
- Remind the subjects to bring all devices currently used (i.e. Accu-Chek® Solo system, mylife™ OmniPod® system, Accu-Chek® blood glucose meter /Accu-Chek® Smart Pix compatible meter) with them to the next visit
- Record all relevant data in the eCRF

### **7.4 Visit 3 – Middle of parallel phase (week 13 [± 14 days])**

Study procedures include the following assessments:

- Record any changes in diabetes medication
- Record any changes in diabetes-associated diseases and treatment

---

 Study devices may be handed-out prior visit 2 if this is required for training purposes.

## CONFIDENTIAL

- Record any changes in concomitant medications
- Record any malfunctions /incidents
- Assess and record any new AE/SAEs and/or changes in ongoing AE/SAEs since the previous visit
- Obtain information on hypoglycemic events and time of absence from work or school due to diabetes complications
- Have subjects complete questionnaires
- Obtain and record weight
- Draw blood sample for determination of HbA1c (in central laboratory)
- Perform urine pregnancy test in women of child bearing potential (only if applicable by local law, e.g. in Austria)
- Examine insertion sites and record signs of redness, swelling, heat, pain and itching according to the categories as listed (none, minor, moderate, severe)
- Download data from the devices used since previous visit
- Hand-out new study material, collect used study material and register study material accordingly:
  - consumables and other supplies
- Make appointment for the next visit
- Remind the subjects to bring all devices currently used (e.g. Accu-Chek® Solo system, mylife™ OmniPod® system, Accu-Chek® blood glucose meter /Accu-Chek® Smart Pix compatible meter) with them to the next visit
- Record all relevant data in the eCRF

### **7.5 Visit 4 – End of parallel phase (week 26 [± 14 days])**

Study procedures include the following assessments:

- Record any changes in diabetes medication
- Record any changes in diabetes-associated diseases and treatment
- Record any changes in concomitant medications
- Record any malfunctions /incidents
- Assess and record any new AE/SAEs and/or changes in ongoing AE/SAEs since the previous visit.
- Obtain information on hypoglycemic events and time of absence from work or school due to diabetes complications
- Have subjects complete questionnaires
- Obtain and record weight
- Draw blood sample for determination of HbA1c (in central laboratory)
- Perform urine pregnancy test in women of child bearing potential (only if applicable by local law, e.g. in Austria)
- Examine insertion sites and record signs of redness, swelling, heat, pain and itching according to the categories as listed (none, minor, moderate, severe), if applicable
- Download data from the devices used since previous visit
- Perform and document training for the Accu-Chek® Solo micropump system study devices and procedures, see section 7.9

- Collect and register study materials and return to Sponsor:
  - Group A: Study device if previously using non-CE marked device
  - Group B: Study device, remaining consumables and other supplies
  - Group C: Study device, remaining consumables and other supplies
- Hand-out new study material and register study material accordingly:
  - New study device(s), consumables and other supplies
- Provide instructions with regard to:
  - Handling of any malfunctions and contact to local Call Center (hand out call center card)
- Make appointment for the next visit
- Remind the subjects to bring all devices currently used (Accu-Chek® Solo micropump system) with them to the next visit
- Record all relevant data in the eCRF

## **7.6 Visit 5 - Final Visit (week 39 [ $\pm$ 14 days]) or Early Termination Visit**

Study procedures include the following assessments:

- Record any changes in diabetes medication
- Record any changes to other medications
- Record any malfunctions /incidents
- Assess and record any new AE/SAEs and/or changes to ongoing AE/SAEs since the previous visit
- Obtain information in hypoglycemic events and time of absence from work or school due to diabetes complications
- Have subject complete questionnaires
- Obtain and record weight
- Draw blood sample for determination of HbA1c (in central laboratory)
- Perform urine pregnancy test in women of child bearing potential (only if applicable by local law, e.g. in Austria)
- Examine insertion sites and record signs of redness, swelling, heat, pain and itching according to the categories as listed (none, minor, moderate, severe), if applicable
- Download data from the devices used since previous visit
- Collect and register study material and return to sponsor:
  - Study device(s), remaining consumables and other supplies
- Record all relevant data in the eCRF

---

 Study devices may be handed-out prior visit 4 if this is required for training purposes.

 All non-CE marked material must be collected. In case the subject was using CE-marked material, is willing to continue therapy with Accu-Chek Solo and proper medical support can be assumed, only used Accu-Chek Solo pump bases must be collected.

## 7.7 Follow-up Call

This follow-up phone call takes place 2-5 days after visit 5 if ongoing AEs or SAEs including but not limited to skin reactions have been recorded at this visit. Record all relevant data obtained at the follow up call in the source data and the eCRF.

## 7.8 Unscheduled Study Visits or Phone Calls

During the course of the study, subjects may require additional (unscheduled) visits with their physicians (Investigators) for any number of reasons including, but not limited to the following:

- Routine visits according to local practice
- Medication adjustment for diabetes and/or other diseases
- Adverse Events/Severe Adverse Events

Full documentation of the visit including any assessments or examinations performed should be maintained in the source documents.

## 7.9 Training of Subjects

In order to prepare subjects for their study procedures, they will be trained in the following:

- All subjects will receive general diabetes training including carbohydrate counting at visit 2 – Baseline Visit
- All subjects will receive general insulin pump training when switching from MDI to CSII (groups A & C at visit 2 - Baseline, group B at visit 4 - End of parallel phase).
- All subjects switching therapy will receive pump therapy optimization during a run-in phase of up to 2 weeks after switching from MDI to CSII.
- Subjects will receive training for the Accu-Chek® Solo micropump system when switching to this pump system (group A at visit 2 - Baseline, groups B & C at visit 4, End of parallel phase).
- Subjects will receive training for mylife™ OmniPod® when switching to this pump system (group C at visit 2 - Baseline).

All trainings will be done according to the established standard for pump therapy of the respective site.

Both carbohydrate count training (for all groups) and insulin pump trainings (for groups A & C) required during visit 2 – Baseline may be started after randomization at visit 1 – Screening. Insulin pump training required during visit 4 – End of parallel phase (for group B) may be started up to one week prior to this visit and must be completed at the end of the run-in phase.

The sites will be trained in the use of the Accu-Chek® Solo micropump system by the Sponsor. Training for subjects will be according to local routine.

The sites will use their own, established mylife™ OmniPod® training for subjects in group C.

Both planned ambulant contacts and planned hospitalizations for training purposes will be considered non-captured adverse events.

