### **11.3 Handling of subject withdrawals and missing values**

As described in 11.2, all randomized subjects will be part of the FAS group and thus be utilized for primary analysis. The pink (left) part of the DTQ will be assessed before randomization. This will guarantee that no bias will be introduced by a possible preference of subjects for a particular group, resulting in a possible withdrawal of individual subjects right after randomization.

For subjects that answered DTQ during Visit 4, these answers will be used for the primary analysis.

The following steps are planned to avoid missing data:

- In case of withdrawal, subjects will be asked to answer the DTQ questionnaire during the End of Study visit.
- If it will not be possible to get questionnaire results at the End of Study visit but questionnaire results are available from week 13 (visit 3), these results will be used, i.e. a LOCF procedure will be applied.
- If there will be no results from week 13, e.g. because a subject will withdraw before week 13, a value of 3 (“Same”) will be imputed as the answer to every individual question. This will result in a total score of 90 (30 times 3), which corresponds to the assumed mean result for the MDI group and thus represents a conservative imputation (the anticipated mean score for the Accu-Chek® Solo group is 110).

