## 2.5. Primary efficacy endpoints

The primary goal of the study is to assess, if treatment satisfaction in the Accu-Chek® Solo group (Group A) increases in comparison to the group using MDI (Group B) and to the mylife™ OmniPod® group (Group C). Change in treatment satisfaction will be assessed by Part 1, "Impact and Satisfaction" of the Diabetes Technology Questionnaire (DTQ). This question-naire

consists of two parts of identical questions, the status part (“Is this a problem now?”) and the change part (“How has it changed compared to your treatment before the study?”). For the current study, the change part (“How has it changed compared to your treatment before the study?”) will be used as primary variable with the status part as covariate.

The status part can be answered with a rating between 1 (very much) and 5 (not at all), the change part with a rating between 1 (much worse) and 5 (much better). For both parts, the sum of all individual answer scores will be used for analysis.

The change score as dependent variable will be analyzed with an Analysis of Covariance (ANCOVA) with group as independent variable and the status (“Is this a problem now?”) answers of the DTQ assessed at Visit 1 (V1) and the site as covariates.

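### Solo training and device hand-out may precede Visit 4, and nothing requires the primary DTQ to be completed first in the comparator arms

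*Protocol*

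**What the plan says.** **Training.** Protocol 7.9 schedules training on the Solo system for "group A at visit 2 - Baseline, groups B & C at visit 4, End of parallel phase". It lists general pump training separately, at Visit 4 for group B. It then says that the pump training required at Visit 4 for group B "may be started up to one week prior to this visit and must be completed at the end of the run-in phase".

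**Hand-out.** Footnote 6, attached to the hand-out item in Protocol 7.5, adds: "Study devices may be handed-out prior visit 4 if this is required for training purposes". It names no group and sets no limit on how early.

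**Visit 4 itself.** Protocol 7.5 lists "Have subjects complete questionnaires" ahead of "Perform and document training for the Accu-Chek® Solo micropump system study devices and procedures, see section 7.9" and ahead of the hand-out of new material. No sentence makes that order a requirement.

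**Primary endpoint.** Protocol 11.3: "For subjects that answered DTQ during Visit 4, these answers will be used for the primary analysis". SAP 3.4.1 repeats this. The change items ask "How has it changed compared to your treatment before the study" (SAP 2.5). SAP 2.2 says that there is no blinding.

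**SAP on timing.** SAP 3.5.4.1 assumes that arms B and C do not receive Solo until Visit 4. It has no rule for earlier exposure.

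**The concern.** The primary outcome is a self-rating in an open-label trial. A group B subject may spend up to a week learning the pump that is about to replace injections, and then answer the questionnaire meant to measure satisfaction with injections. Two mechanisms are plausible. The subject may mark injections down by contrast with Solo, or may partly credit Solo in the answers, because the change item as quoted names the reference treatment but not the treatment being rated.

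Group A already uses Solo, so it has no comparable first exposure. Any effect would sit in a comparator arm only. Randomisation and adjustment for the Visit 1 DTQ status score would not remove it, because the exposure comes after both.

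**Working it through.** **1. Can exposure come before the primary DTQ?**

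| Step | Group B (MDI) | Group C (OmniPod) |
|---|---|---|
| Pump received at Visit 4 (Protocol 2.1) | Solo | Solo |
| Early training permitted in 7.9 | Yes, up to one week | Not mentioned |
| Early hand-out under footnote 6 | Not excluded | Not excluded |
| Rule that the DTQ comes first | None | None |

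The list order in 7.5 concerns the visit. It cannot protect a questionnaire answered at Visit 4 from training or hand-out some days earlier. The route is clear for group B. For group C it rests on footnote 6 alone.

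**2. Do the documents agree?** Footnote 6 permits hand-out before Visit 4, while SAP 3.5.4.1 assumes there is none. They need reconciling whatever the size of any bias.

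**3. The plan's own sample size.** Inputs from Protocol 11.1: means 90 and 110 (difference 20), SD 30, two-sided alpha 0.05, power 90%, drop-out 18%.

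- Normal approximation: n = 2 × (1.960 + 1.282)² × 30² / 20² = 47.3, so 48 per group.
- Two-sample t-test: n = 48.26, so 49 per group, which matches the plan.
- Drop-out: 49 / 0.82 = 59.8, so 60 per arm, which also matches.

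**4. Effect of an assumed shift on the first comparison.** The documents give no shift. Assume 0.1 per item: 30 × 0.1 = 3 points on the sum, or 3 / 20 = 15% of the planned difference. Power comes from the noncentral t with 96 degrees of freedom, noncentrality (difference / 30) × √(49/2) and critical value 1.985.

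| Mean shift in group B | Apparent difference | Noncentrality | Power |
|---|---|---|---|
| none | 20 | 3.30 | 90.4% |
| up 3 | 17 | 2.80 | 79.3% |
| down 3 | 23 | 3.79 | 96.4% |
| up 1 | 19 | 3.13 | 87.4% |
| down 1 | 21 | 3.46 | 92.9% |

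The 1-point rows are the case where one third of the arm is exposed and each exposed subject shifts by 3 points (3 × 1/3 = 1).

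**5. With no true difference.** The nominal chance of a significant result favouring Solo is 2.5%. If the comparator arm's mean is lowered by 3 points, it is 7.1%; by 6 points, 16.4%. These are single-comparison figures. They apply to the OmniPod comparison only if group C is exposed, and only once the first comparison has been passed.

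**The case against.** **Early Solo content is inferred.** Section 7.9 separates general pump training from Solo training, and the early-start sentence does not name Solo. This is correct. The inference rests on Solo being the only pump group B receives and on footnote 6 allowing devices out for training. The text permits early exposure but does not require it, and how often it occurs is unknown. Nothing says that insulin delivery by Solo starts early.

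**Anticipation is built into the design.** Every subject in B and C knows that Solo follows at week 26, and reordering the questionnaire cannot change that. This stands. Only the increment from hands-on exposure is at issue. The anchor to pre-study treatment limits a contrast effect but does not exclude one.

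**Group A is not wholly static.** Protocol 7.5 provides for collecting a non-CE-marked device from group A at Visit 4. It is the same system, and Protocol 3.3 calls the differences minor, so this is not an equivalent exposure.

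**Stronger readings that a reader might infer.**

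- *The bias runs in one direction, favouring Solo.* The two mechanisms above have opposite signs, and the documents support neither over the other.
- *Sections 7.9 and footnote 6 override the order in 7.5.* They are permissions. They leave the order within the visit alone and do not forbid completing the DTQ first.
- *Both primary comparisons are affected equally.* Early training in 7.9 is confined to group B, and the SAP describes B and C as receiving Solo no earlier than Visit 4.
- *The sponsor guarded the baseline DTQ against this same influence.* Protocol 11.3 does fix that the initial "part of the DTQ will be assessed before randomization", but the stated reason is group preference leading to withdrawal just after randomisation. It shows that sequence can be fixed, not that this protection was forgotten at Visit 4.

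**Conclusion.** The point holds as a sequencing gap that should be closed. Following the plan as written, a group B subject can answer the primary DTQ after Solo training and handling. A group C subject may be able to, on the weaker support of footnote 6. The conflict between that footnote and SAP 3.5.4.1 is established by the text alone.

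The size is not established. The 79% and 96% figures assume a 3-point mean shift over the whole MDI arm, 49 evaluable subjects per arm, SD 30 and a t-test in place of the planned ANCOVA. The effect shrinks with the fraction exposed. The documents do not show that any subject was exposed early, or that the result is biased towards Solo.

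**What to change.** **Protocol.** Add to 7.5, 7.9 and footnote 6: in groups B and C, the week-26 DTQ and the other questionnaires are completed before any Solo training or hand-out of the Solo system. If training starts early, they are completed at that first contact. That contact counts as the Visit 4 questionnaire only if it falls within week 26 ± 14 days. This condition is needed because a contact 7 days before a Visit 4 held at day −14 would be at day −21, and footnote 6 has no time limit at all.

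**SAP.** Reconcile 3.5.4.1 with footnote 6.

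**Data already collected.** SAP 6.13.1 (version 1.2) places the study in its final phase, so wording alone may come too late. Compare the dates of first Solo training and hand-out with the DTQ date where these are recorded. Report the number of subjects exposed before the DTQ by arm, and add a sensitivity analysis of the primary ANCOVA for those subjects.

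**Cost.** A wording amendment with ethics submission (Protocol 12.7), a site reminder, and one additional analysis. The questionnaires are electronic and completed at the site. Sample size stays at 49 evaluable and 60 enrolled per arm.

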## 7.10 Subject Questionnaires (to be completed at the site)

Subjects will be asked to complete several questionnaires at each visit. These questionnaires will be presented electronically. Thus, study staff will open subject's file in the eCRF-system, open the questionnaires, and hand over to the subject with a short explanation as to completion.

When the subject has finished he/she should "save" and close the document.

Hereafter, neither Investigator nor study staff will be able to see the subject's entries, and thus, confidentiality is ensured.

Study questionnaires can be grouped thematically:

- Questionnaires regarding the subject's psychological situation,
- Questionnaires assessing device parameters,
- Questionnaires assessing training.

The following table lists the timing of the subject questionnaires as per their treatment group (A, B, or C):

Questionnaire \ Visits	Visit 1 Screening	Visit 2 Baseline	Visit 3	Visit 4	Visit 5
DTQ, Initial	A, B, C				
DTQ, Difference			A, B, C,	A, B, C	A, B, C
PAID-5	A, B, C		A, B, C	A, B, C	A, B, C
Roche-Specific			A	A	A, B, C
Roche-Specific without questions 8&9			C	C	

## 7.11 Subject Diaries

No study specific diary for will be required.

## 7.12 Laboratories

### 7.12.1 Local Laboratories

Blood samples must be drawn for the determination of the following parameters at the site's local laboratory according to local practice:

- HbA1c

Please note that a previous result may be used if less than 2 months prior to Visit 1.

The following urine tests will be performed at the site's local laboratory at Visit 1- Screening:

- Pregnancy test, if applicable and at every visit if required by local law, e.g. Austria. The pregnancy tests will be provided by the Central Laboratory

